6.4 STUDY INTERVENTION COMPLIANCE

To ensure maximum compliance, all doses of study drug solution will be administered by study staff.

Source documents will be completed with all relevant information. These will include: dose, time, vital signs (pre and post injection) and any side effects if occurred during procedures.

6.5 CONCOMITANT THERAPY

Not applicable

6.5.1 RESCUE MEDICINE

Not applicable

7 STUDY INTERVENTION DISCONTINUATION AND PARTICIPANT DISCONTINUATION/WITHDRAWAL

7.1 DISCONTINUATION OF STUDY INTERVENTION

Participant will be discontinued from the study if they are not able to lie on their back in the scanner table for 15-20 during the procedure or if they suffer from claustrophobia. This will be documented in the CRF with date and specific reason for discontinuation of the participant.

7.2 PARTICIPANT DISCONTINUATION/WITHDRAWAL FROM THE STUDY

Participants are free to withdraw from participation in the study at any time upon request.

An investigator may discontinue or withdraw a participant from the study for the following reasons:

- Significant study intervention non-compliance
- If any clinical adverse event (AE), laboratory abnormality, or other medical condition or situation occurs such that continued participation in the study would not be in the best interest of the participant
- Disease progression which requires discontinuation of the study intervention
- If the participant meets an exclusion criterion (either newly developed or not previously recognized) that precludes further study participation

The reason for participant discontinuation or withdrawal from the study will be recorded on the Case Report Form (CRF). Subjects who sign the informed consent form and are screened but do not receive the study intervention may be replaced. Subjects who sign the informed consent form, and are screened and receive the study intervention, and subsequently withdraw, or are withdrawn or discontinued from the study, will not be replaced.

7.3 LOST TO FOLLOW-UP

A participant will be considered lost to follow-up if he or she fails to return for scheduled visits and is unable to be contacted by the study site staff.

The following actions must be taken if a participant fails to return to the clinic for a required study visit:

- The site will attempt to contact the participant and reschedule the missed visit, during the following week and counsel the participant on the importance of maintaining the assigned visit schedule and ascertain if the participant wishes to and/or should continue in the study.
- Before a participant is deemed lost to follow-up, the investigator or designee will make every effort to regain contact with the participant (where possible, 3 telephone calls and, if necessary, a certified letter to the participant's last known mailing address or local equivalent methods). These contact attempts should be documented in the participant's medical record or study file.
- Should the participant continue to be unreachable, he or she will be considered to have withdrawn from the study with a primary reason of lost to follow-up.

8 STUDY ASSESSMENTS AND PROCEDURES

8.1 EFFICACY AND SAFETY ASSESSMENTS

8.1 Informed Consent

All subjects must sign and personally date an IRB approved informed consent form after receiving detailed written and verbal information about the reason, the nature and the possible risks associated with the administration of the study agent prior to the initiation of any study-related procedures. This must be done according to the guidelines provided in the Declaration of Helsinki, ICH E6 Guideline for Good Clinical Practice (GCP), and requirements of Title 21 CFR 50.20 through 50.27. The subject must be made aware and agree that personal information may be scrutinized during an audit by competent authorities and properly authorized persons. However, personal information will be treated as strictly confidential and will not be publicly available.

8.2 Medical History

A complete medical history, including prostate cancer history, will be obtained at the first screening visit. Site staff will record the subject's medical history in the subject's source records and transcribe the information onto the medical history section of the CRF. Historical information concerning allergies (including food, drug and/or environmental) will also be obtained.

8.3 Vital Signs

Vital signs will include measurement of blood pressure and heart rate. Vital signs will be obtained and recorded at the Screening visit, pre- and post- each study drug injection, and also 2 hours after the first injection.

8.4 Dispensing Study Drug

The radiopharmaceutical will be injected through the indwelling catheter at a 185 ± 74 MBq (5 ± 2 mCi) dose. The estimated radioactive dose will be determined by measuring the amount of radioactivity in the syringe pre- and post-injection, using an appropriately calibrated radioisotope dose calibrator in accordance with the nuclear medicine department's SOPs. The injected activity will be recorded in the subject's source records and transcribed into the CRF.

The injection will be given by slow intravenous bolus. Following completion of the 68Ga-PSMA-11 injection, a normal saline flush (approximately 10 mL) will ensure that all 168Ga-PSMA-11 remaining in the infusion line is injected.

Any administration complication of the drug (e.g., overdose, observable extravasation, medication error) will be reported to the Chief of Nuclear Medicine and the PI within 24 hours of the event and will be recorded in the subject's source records and transcribed onto the CRF. If the Chief of Nuclear Medicine and the PI determine an adverse event occurred after injection or because of extravasation this will be reported as outlined in **Section 7**.

8.5 Computed Tomography (CT) and Magnetic Resonance (MR) Imaging

A diagnostic quality MR scan (abdomen and pelvis) may be obtained (if clinically indicated) prior to surgery if not done within 6 months of the screening visit, if clinically indicated. If collected as part of screening procedures, the scan should be contrast-enhanced, unless contra-indicated for the subject. If necessary, the scan maybe obtained between the first injection of study drug and surgery.

8.6 Bone Scan

If clinically indicated, a bone scan may be obtained prior to surgery if not done within 6 months of the screening visit. If necessary, the scan may be obtained between the first injection of study drug and surgery.

8.7 68Ga-PSMA-11 PET/CT Imaging

A whole-body positron emission tomography/Computed Tomography (PET/CT) scan will be obtained between 60-90 minutes post-injection of study drug.

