1 PROTOCOL SUMMARY

1.1 SYNOPSIS

Title:	Comparison of 68Ga-PSMA Positron Emission Tomography (PET)/CT to Conventional Imaging in Men with High Risk Prostate Cancer
Study Description:	This is a prospective, single-center, open-label pilot study of 68GA-PSMA-11 given at a single time prior to PET/CT imaging in men with localized high risk prostate cancer or biochemical recurrence. Eligible participants will undergo baseline assessments using conventional 99-Tc Bone Scan and CT of the Abdomen and Pelvis or multi-parametric MRI imaging of the prostate

Objectives:

Primary Objective

1. To evaluate the tissue distribution of 68GA-PSMA-11 PET/CT imaging in normal tissues and biopsy proven tumor and non-tumorous regions of the prostate, and also pelvic lymph nodes in high risk patients undergoing standard of care prostatectomy and bilateral lymph node dissection.
2. To determine the proportion of patients in which 68GA-PSMA-11 PET/CT altered the planned clinical management.

Secondary Objective:

1. To correlate the intensity of 68GA-PSMA-11 PET/CT uptake with respect to pathological findings.
2. To compare suspicious lesions visualized on 68GA-PSMA-11 PET /CT with standard of care diagnostic imaging modalities, additional biopsy results, or clinical follow-up performed at the discretion of the referring physician.

Endpoints:

Primary Endpoints:

1. Proportion of patients with cTxNoMo (clinically localized disease) found on final histological examination to have lymph node involvement as determined by 68GA-PSMA-11 PET/CT.
2. Proportion of patients in which 68GA-PSMA-11 PET/CT altered the planned clinical management.

Secondary Endpoints:

1. 68GA-PSMA-11 PET/CT intensity is variable, and we will evaluate what intensity endpoint is predictable of tissue involvement.
2. To compare and contrast findings in 68GA-PSMA-11 PET/CT with standard diagnostic modalities of bone scan, CTs and MRIs.

Study Population: Male patients, aged 21 or older, diagnosed with histopathological proven prostate adenocarcinoma, with no evidence of other malignancy, and Eastern Cooperative Oncology Group (ECOG) performance of 0-1.

Phase: Pilot, phase I/2

Description of Sites/Facilities
This is a single site trial that will be conducted at the Houston Methodist Hospital.

Enrolling Participants:

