1.2 SCHEDULE OF ACTIVITIES (SOA)

The schedule below is provided as an example and should be modified as appropriate.

	Screening	Enrollment	Post Dose		Surgery/Pre-surgery Follow up/Early Termination	Follow up	Follow up
	Day -28 to 0	Day 0	Day 0: Hour 1-2	Day 2	Day 10 +/- 7	Month 2 +/- 7	Month 6 +/- 7
	Visit 1	Visit 2		Phone call		Visit 3	Visit 4
Informed Consent	R						
Demographics	R						
Inclusion/Exclusion Criteria	R						
Medical History ¹	R						
Performance Status	R						
Vital Signs ²	R		R ³				
Administer Study Intervention 68Ga PSMA 11		R					
Whole body PET/CT		R					
PSA	R					SOC	SOC
Bone Scan ⁴	SOC						
CT abdomen/pelvis ⁴	SOC						
MRI of prostate	SOC						
Adverse event evaluation			R	R	R		
Prostate Biopsy	SOC						
Telephone call				R			
Prostatectomy					SOC		

Pathology processing					SOC	
----------------------	--	--	--	--	-----	--

¹ *Medical history includes review of prostate cancer treatment and prior radiographic exams.*

² *Vital Signs Assessment includes measurement of blood pressure and heart rate.*

³ *On days of dosing, vital signs will be collected pre-dose and post-dose.*

⁴ *If not performed within 6 months of Screening, diagnostic CT or MR scans and or Bone scan are to be obtained prior to surgery, only if clinically indicated*

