6.3 MEASURES TO MINIMIZE BIAS: RANDOMIZATION AND BLINDING

To minimize bias, all PET/CT images will be interpreted by a board-certified radiologist. The radiologist evaluating the images will be blinded to the final outcome, such as the histopathology of any biopsies and the outcome of subsequent imaging.

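### Conventional scans done after the PSMA injection are not excluded from secondary endpoint 2, so PET could prompt or guide the imaging it is compared with

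*Combined protocol and SAP*

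**What the plan says.** Section 8.6 gives the condition for a new bone scan: "If clinically indicated, a bone scan may be obtained prior to surgery if not done within 6 months of the screening visit". It then adds that, if necessary, "the scan may be obtained between the first injection of study drug and surgery". Section 8.5 says the same of MR of the abdomen and pelvis: "If necessary, the scan maybe obtained between the first injection of study drug and surgery". Footnote 4 of the Schedule of Activities (section 1.2) covers men with no scan within 6 months of screening and includes CT: "diagnostic CT or MR scans and or Bone scan are to be obtained prior to surgery, only if clinically indicated". Its deadline is surgery, not the injection.

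Two other places read differently. The synopsis (section 1.1) describes conventional imaging as part of the baseline work-up, and the schedule table lists bone scan, CT and MRI in the Screening column.

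Secondary endpoint 2 is: "To compare and contrast findings in 68GA-PSMA-11 PET/CT with standard diagnostic modalities of bone scan, CTs and MRIs". It sets no limit on when the conventional scan is made. On blinding, section 6.3 says: "The radiologist evaluating the images will be blinded to the final outcome". Section 4.1 is to the same effect. Both concern the PET reader, and nothing is said about readers of CT, MR or bone scans.

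**The concern.** PET/CT is done 60-90 minutes after injection, so almost all of the interval between injection and surgery falls after the PET. The PET result is open to the treating team, because the synopsis expects it to alter management. No section requires the clinical indication for a conventional scan to predate the PET. A positive PET can therefore be the reason for the scan, and its location can direct the reader.

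Two biases could follow in secondary endpoint 2. A conventional read aimed at a known PET focus overstates what that modality finds by itself. If scans are ordered more often after a positive PET, the compared sample is also enriched in PET-positive men. Section 3 justifies this endpoint by asking whether the modalities are complementary or whether one could be dropped from the work-up. PET-guided conventional reads cannot answer that question.

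**Working it through.** **Text check**

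- *Timing.* Sections 8.5 and 8.6 and footnote 4 permit scans up to surgery. The synopsis and the Screening column imply scans before injection. These passages conflict.
- *Who is affected.* Only men with no scan within 6 months of screening and with a clinical indication.
- *Comparator.* Endpoint 2 neither includes nor excludes post-injection scans. Their entry is an inference from the missing limit.
- *Shielding.* The PET reader is blinded to subsequent imaging, so the PET read is protected. The conventional read is not.

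The plan has no figure to reproduce: section 9.1 says the sample size of up to 80 was not statistically determined, and section 9.3.1 specifies descriptive statistics only.

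**Illustration 1: directed reading**

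All inputs are assumptions:

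- s = 0.5, conventional detection of PET-visible lesions when read alone. Section 2.1 gives 30-80%, but that is CT/MRI sensitivity for nodal metastasis. It is only a loose guide here and says nothing about bone scan.
- f = 0.10 to 0.40, share of men with no pre-PET scan, all of them scanned after PET.
- h = 0.5, share of otherwise missed lesions called once the PET is known.

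Apparent detection = s + f × (1 − s) × h.

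- f = 0.10: 0.5 + 0.10 × 0.5 × 0.5 = 0.525
- f = 0.40: 0.5 + 0.40 × 0.5 × 0.5 = 0.600

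With s = 0.3 the range is 0.335 to 0.440. With s = 0.8 it is 0.81 to 0.84.

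**Illustration 2: selective ordering**

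These inputs are also assumptions:

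- q = 0.20, the PET-positive rate
- f = 0.25
- a and b, the chance of a scan after a positive and after a negative PET, for men with no earlier scan

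PET-positive share of the compared sample = [(1 − f)q + f·q·a] / [(1 − f) + f(q·a + (1 − q)b)].

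- a = 0.9, b = 0.2: (0.150 + 0.045) / (0.75 + 0.085) = 0.195 / 0.835 = 0.234, about 23%
- a = 1, b = 0 (the extreme): (0.150 + 0.050) / (0.75 + 0.050) = 0.200 / 0.800 = 25%

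**The case against.** The strongest reply is that no section says a post-injection scan will be the comparator. The synopsis and schedule table treat conventional imaging as baseline, and section 9.3.1 leaves detailed procedures to a SAP. This stands against a reader who infers that the plan uses post-PET scans as the comparator: the documents only fail to exclude them. It does not close the gap, because the combined document contains no rule that would.

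A second reply is that secondary objective 2 starts from lesions suspicious on PET and admits later biopsy or follow-up at the referring physician's discretion. Some dependence on PET is therefore built into the objective, and sections 8.5 and 8.6 do not create it. This stands, and it is a reason to separate the head-to-head comparison from the work-up of PET findings.

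Third, a reader might infer that conventional misses in general would be scanned again after PET. The clauses do not support that: a man with a negative scan within 6 months of screening is outside them. The relevant share is men with no qualifying scan, which is why f is used above. The clauses also speak of surgery, so they set no window for men with biochemical recurrence who have no operation.

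Fourth, the endpoint is descriptive, with no defined metric or unit, in a pilot. No error rate is at stake. This limits the severity.

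**Conclusion.** The concern holds as a gap in the definition of the comparator, together with a conflict between sections. Followed as written, the plan lets PET prompt or guide some of the conventional scans it is compared with, and nothing keeps those scans out of secondary endpoint 2.

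The true size is unknown, because the documents do not give the share of men scanned after PET. Under the stated assumptions, directed reading moves an apparent conventional detection of 50% to 52.5-60%. Selective ordering moves a 20% PET-positive share to about 23%. The 25% figure is a ceiling that requires no man with a negative PET and no earlier scan to be scanned at all, so it should not be read as the expected effect. The two effects need not cancel.

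Possibly only a minority of men are affected, and the endpoint is secondary and descriptive. The change is still worth making, because it is cheap and cannot be made neutrally once PET results are known.

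**What to change.** In secondary endpoint 2, state that the head-to-head comparison with conventional imaging uses only CT, MR and bone scans acquired and reported before the Day 0 injection. A report that predates the PET cannot be influenced by it, so this removes both biases. A PET-blinded re-read would deal with the reading but not with the ordering.

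Record the date and indication of every conventional scan. Report post-injection scans separately, as work-up or follow-up of PET findings under secondary objective 2. Carry the rule into sections 8.5 and 8.6 and footnote 4 of the Schedule of Activities, and reconcile those passages with the synopsis and the Screening column. The change concerns only which scans count in the comparison. Whether and when scans are done for care is unchanged.

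The cost is a few sentences and a date check in the dataset. Men with no pre-injection scan leave the head-to-head comparison: 0.10 × 80 = 8 to 0.40 × 80 = 32 of 80 men, if 10-40% lack one. Their number should be reported.

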8.7.1 Imaging Procedures

68-Ga-PSMA PET/CT positivity or negativity will be interpreted, stratified by different anatomic regions as previously defined[1].

REGION	DESCRIPTION
1	Prostate/Prostate Bed
2	Pelvis, excluding prostate bed, but including lymph nodes
3	Extra-pelvic soft tissue, including lymph node involvement and metastasis to other organs
4	Bone Metastasis

The presence of prostate cancer (positive or negative) will be reported within these regions.

A. **Lymph nodes** - considered positive if the 68Ga-PSMA-11 uptake is localized/focal and is greater than the adjacent or mediastinal blood pool. The location of the lymph nodes will be recorded according to one of 7 sub-categories as previously defined[1]:

1	Right Hypogastric/Internal-iliac
2	Left Hypogastric/Internal-iliac
3	Right Obturator
4	Left Obturator
5	Right External-iliac
6	Left External-iliac
7	Other

- B. **Visceral lesions** – These will be considered positive if the 68Ga-PSMA-11 uptake is focal and greater than the physiologic background activity in the organ of interest.
- C. **Bone lesions** – These will be considered positive if the 68Ga-PSMA-11 uptake is focal and greater than physiologic background activity in normal bone marrow.
- D. **Prostate bed** – These will be considered positive if the 68Ga-PSMA-11 activity is focal and greater than the physiologic, background activity in the prostate bed.

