5 STUDY POPULATION

5.1 INCLUSION CRITERIA

- 1) Male aged 21 years or older
- 2) Ability to understand and provide written informed consent
- 3) All patients must have histopathological proven adenocarcinoma of the prostate
- 4) ECOG performance status 0-1
- 5) No evidence of other malignancy (except squamous or basal cell skin cancers)
- 6) Consent to use acceptable form of birth control following the imaging period (condoms for a period of seven days after injection if sexually active)

7) a) inclusion criteria specific for the pre-prostatectomy group:
Untreated prostate Cancer with high-risk features, as defined as having at least one of the following criteria:

- i. PSA \geq 20.0 ng/mL
- ii. ISUP Gleason Grade Group 3, 4 or 5
- iii. Clinical stage T3

b) inclusion criteria specific for biochemical recurrence:

- (i) Histopathological proven prostate adenocarcinoma
- (ii) Rising PSA after definitive therapy with prostatectomy or radiation (therapy (external beam or brachytherapy)).

1. Post radical prostatectomy (RP), PSA greater than or equal to 0.2 ng/ml measured more than 6 weeks after RP.
2. Post-radiation therapy, PSA that is equal to or greater than 2 ng/ml rise above PSA nadir

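### In pre-prostatectomy men the single Region 1 call gives only a detection rate, and uptake in non-tumorous prostate is not captured

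*Combined protocol and SAP*

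**What the plan says.** Primary objective 1 (Synopsis 1.1 and Section 3) concerns tracer distribution in normal tissues, in "biopsy proven tumor and non-tumorous regions of the prostate", and in pelvic nodes. Section 9.1 justifies the 80 patients by the same tumour versus non-tumour evaluation.

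The reading scheme is in Section 4.1 and again in Section 8.7.1. Region 1 is "Prostate/Prostate Bed", undivided, and the scale is binary: "The presence of prostate cancer (positive or negative) will be reported within these regions". Only nodes are localised further: "The location of the lymph nodes will be recorded according to one of 7 sub-categories as previously defined". Positivity rules are given for nodes, viscera, bone and the prostate bed. The last reads: "These will be considered positive if the 68Ga-PSMA-11 activity is focal and greater than the physiologic, background activity in the prostate bed". No rule is written for an intact gland.

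Section 5.1 requires of everyone: "All patients must have histopathological proven adenocarcinoma of the prostate". The pre-prostatectomy group must have "Untreated prostate Cancer with high-risk features". The recurrence group has a rising PSA after prostatectomy or radiation.

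Two other sections bear on the prostate. Section 8.7.1.2 plans manual regions of interest (ROIs) with SUVmean and SUVmax around listed major organs, which do not include the prostate, and around other tissue where uptake can be seen. Section 8.9 makes tumour foci on H&E sections the reference standard and adds immunohistochemistry to confirm co-localisation.

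**The concern.** A binary call on a region that is diseased in every man cannot separate a discriminating test from one that is always positive. In the surgical cohort the Region 1 result says how often the prostate lights up. It says nothing about uptake in benign prostate, false-positive foci, or whether the avid area is where the tumour is.

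This matters because primary objective 1 names non-tumorous prostate, and secondary endpoint 1 looks for the intensity that predicts tissue involvement. Both need measurements in uninvolved tissue as well as involved tissue. If sector-level calls are not recorded at the blinded read, later analysis cannot recover them without a fresh blinded re-read.

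**Working it through.** The plan has no derived figure to reproduce. Section 9.1 says the sample size was not statistically determined, and no alpha, power, effect size or cohort split is given. The check is therefore what each planned measurement can identify.

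**Step 1. The Region 1 call in pre-prostatectomy men.** Take the entry histology as correct. For n men, diseased = n and non-diseased = 0.

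- Specificity = true negatives / non-diseased = 0/0, undefined for every n.
- Positive predictive value = 100% by construction.
- Sensitivity is estimable. Exact (Clopper-Pearson) 95% intervals, with n assumed and 90% detection assumed:

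| n | 90% detected | Reader who calls every gland positive |
|---|---|---|
| 20 | 68.3 to 98.8% | 83.2 to 100% |
| 40 | 76.3 to 97.2% | 91.2 to 100% |
| 80 | 81.2 to 95.6% | 95.5 to 100% |

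A larger n narrows the detection rate but leaves the non-diseased count at zero. The always-positive reader gets the best score.

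**Step 2. What the other elements add.**

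- *SUV (8.7.1.2).* ROIs in avid prostate areas later found to be tumour or not could be compared. Prostate without visible uptake gets no ROI, so the benign tissue sampled is only the part that is already avid. The ROIs are drawn on anterior projections, which lose front-to-back position within the gland.
- *Histology (8.9).* Known tumour foci allow a per-focus detection rate if they can be paired with PET findings. No intraprostatic PET location is recorded, no pairing rule is given, and no tumour-free unit is defined.
- *Recurrence group.* Region 1 can truly be negative here. But no histology is scheduled for these men, and Section 4.1 describes validation for positive scans.

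None of these yields uptake or a false-positive rate for non-tumorous prostate.

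**Step 3. What a sector read would add.** All inputs are assumptions, because the documents give none: n = 20, 40 or 80 operated men; 6 sectors per gland; tumour-free fraction f = 0.3 to 0.7; within-man intraclass correlation (ICC) 0 to 0.5; specificity 80%.

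- Tumour-free sectors per man: m = 6f. Total: n × m.
- Effective number: n_eff = n × m / (1 + (m − 1) × ICC).
- 95% half-width: 1.96 × √(0.8 × 0.2 / n_eff).

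| n | Tumour-free sectors | n_eff | Half-width (points) |
|---|---|---|---|
| 20 | 36 to 84 | 25.7 to 84 | 15.5 to 8.6 |
| 40 | 72 to 168 | 51.4 to 168 | 10.9 to 6.0 |
| 80 | 144 to 336 | 102.9 to 336 | 7.7 to 4.3 |

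Mid-case: n = 40, f = 0.5, ICC = 0.2. Then m = 3 and there are 40 × 3 = 120 sectors. n_eff = 120 / (1 + 2 × 0.2) = 85.7, and the half-width is 1.96 × √(0.16 / 85.7) = 8.5 points.

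**The case against.** A reader might infer that tumour versus non-tumour discrimination in the prostate cannot be estimated at all in this trial. The documents do not support that. The SUV ROIs, the H&E reference and secondary endpoint 1 are real sources of intraprostatic data, and they could give a per-focus detection rate and an SUV comparison among avid areas. Nor is Region 1 without true negatives across the whole study: in recurrence patients the proven cancer is historical, and the bed may be tumour-free.

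It can also be said that the plan never promises intraprostatic specificity. Primary objective 1 is about tissue distribution, primary endpoint 1 is nodal, and Section 4.2 calls the study exploratory. That stands: no specificity endpoint has been missed. But distribution in non-tumorous prostate is named in the objective, and Section 4.1 describes a diagnostic accuracy study. Sampling only visible uptake does not measure that distribution.

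Section 9.3.1 defers detailed methods to a SAP, and no separate SAP text is among the documents, so a sector-level analysis there cannot be excluded. It would still need sector-level readings, which the reading scheme does not collect.

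Finally, Section 8.9 describes standard processing for grading and staging, without sector mapping. Matching may therefore be incomplete or need extra pathology work.

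**Conclusion.** The concern holds within limits. In pre-prostatectomy men the Region 1 call supports a detection rate and nothing more, and this does not depend on n. The SUV and histology plan narrows the gap without closing it, because non-avid prostate is never sampled and no intraprostatic unit or matching rule is set. Primary endpoint 1 is nodal and unaffected. What is exposed is the intraprostatic part of primary objective 1 and, within the prostate, secondary endpoint 1.

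The first conclusion rests only on the entry criteria and the reading scheme. The size of the gain from a sector read rests on an unstated cohort split. The number of operated men may also be below the number entered for surgery, since the Synopsis allows the scan result to lead to surgery not being pursued.

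**What to change.** Amend Sections 4.1, 8.7.1, 8.7.1.2, 8.9 and 9.3 for men who go to prostatectomy:

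1. Have the same blinded reader record positive or negative, and SUV, in each prostate sector (for example sextants) regardless of visible uptake. Complete this before pathology is known, in keeping with Section 6.3. Because it is not yet known at the scan who will be operated on, read all pre-prostatectomy men this way and analyse those with a specimen.
2. State that the focal-above-background rule applies to the intact gland as well as the bed.
3. Match sectors to the location of H&E tumour foci where pathology records it, and report how many sectors could not be matched.
4. Report uptake and positivity in tumour and tumour-free sectors, with intervals that allow for clustering by patient.

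Keep the single Region 1 read for recurrence patients, including those with an irradiated gland in place and no specimen.

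The cost is one sector grid per scan, extra reading time and transcription of tumour location, which depends on what standard pathology reports contain. Some sectors will be misregistered between PET and specimen. Patient care does not change.
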